7.3 Endpoints

Primary endpoint:

The following endpoints will address the primary objective (concerning Saxenda® only):

BMI and comorbidities:

- Number of patients with Body Mass Index (BMI)≥30 kg/m² (measured less than 6 months before date of first prescription).
- Number of patients with 27 kg/m² ≤BMI<30 kg/m² (measured less than 6 months before date of first prescription) and
 - ≥1 relevant comorbidity registered:
 - Dysglycaemia (T2DM or prediabetes), hypertension, dyslipidaemia, and/or obstructive sleep apnoea.
 - o No relevant comorbidities (described above) registered.
- Number of patients with BMI<27 kg/m² (measured less than 6 months before date of first prescription).
- Number of patients with BMI not measured within 6 months before date of first prescription.

 Protocol
 Date:
 23 November 2015
 Novo Nordisk

 Study ID: NN8022-4241
 Version:
 5.0

 UTN: U1111-1185-3661
 Status:
 Final

 EU PAS No.:
 CONFIDENTIAL
 Page:
 17 of 53

Stopping rule:

- Number of patients with at least 5% weight loss (measured 16-24 weeks after first prescription date) and continuing treatment.
- Number of patients with less than 5% weight loss (measured 16-24 weeks after first prescription date) and continuing treatment.
- Mean weight loss (measured 16-24 weeks after first prescription date) in patients not treated according to stopping rule.

Secondary endpoint:

The following endpoint will be used to address the first secondary objective (concerning Victoza[®] only):

- Number of patients with Victoza[®] prescriptions fulfilling at least one of the following criteria:
 - 1. Dose information of 3.0 mg per day, or
 - 2. Indication of weight management.

The following endpoints will be used to address the second secondary objective (concerning Saxenda® only):

- Adherence to dose escalation according to label:
 - o Number of patients who have reached a dose of 3.0 mg within 4-12 weeks after first prescription date.
- Concomitant medication with of other GLP-1 receptor agonists:
 - Number of Saxenda[®] patients with other GLP-1 receptor agonists prescribed during continued treatment with Saxenda[®] (continued treatment is defined as no gaps between prescriptions of more than 90 days, identified by examining repeat prescription dates).
- Duration of treatment with Saxenda®:
 - o Number of patients with a treatment duration of:

Protocol		Date:	23 November 2015	Novo Nordisk
Study ID: NN8022-4241		Version:	5.0	
UTN: U1111-1185-3661		Status:	Final	

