Based on the data obtained in the pilot study, full study refinements may be necessary before the full retrospective medical record review is implemented in the two countries.

The index date, defined as the start date of data abstraction, will be 6 months after the launch of Saxenda[®] for the pilot, and 24 months after launch for the full study (see Figure 1 for an overview of the study design). The launch date may be different in the two countries. The data will be collected only after informed consent has been obtained from the patients. All study prescribers within a country will be assigned the same index date and will not be contacted prior to it. Initiation of prescriber-specific activities for selection of patient records meeting study selection criteria will commence on or following the index date. Data on drug utilisation will be censored on the index date. This approach will ensure that study procedures do not influence prescribing practices.

 Protocol
 Date:
 23 November 2015
 Novo Nordisk

 Study ID: NN8022-4241
 Version:
 5.0

 UTN: U1111-1185-3661
 Status:
 Final

Page:

20 of 53

CONFIDENTIAL

[figure not shown]

Figure 1 - DUS overview

EU PAS No .:

Notes: The index date (start date of data abstraction) for the pilot study will be 6 months following the launch of Saxenda[®] in the participating countries; data will be collected on patients from their start date of Saxenda[®]/Victoza[®] until the index date for the pilot study. The index date for the full study will be 24 months after the launch of Saxenda[®]; data will be collected on patients from their start date of Saxenda[®]/Victoza[®] until the index date for the full study. ICF: Informed Consent Form; M: month

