8.2.6 Flowchart

The data collection period for Saxenda[®]/Victoza[®] will be the interval between the launch date of Saxenda[®] to the index date of the pilot or full study, respectively. Table 1 and Table 2 show the data to be collected respectively for Saxenda[®] and Victoza[®] patients at different time points in relation to initiation of treatment. Data collection will encompass the following treatment periods for Saxenda[®]: (1) a time frame of 6 months prior to treatment initiation, (2) treatment initiation, (3) 4-12 weeks post treatment initiation, (4) 16-24 weeks post treatment initiation, and also (5) throughout the entire treatment period. Data collection will encompass the following treatment periods for Victoza[®]: (1) treatment initiation, and (2) throughout the entire treatment period.

Protocol	UTN: U1111-1185-3661	Date:	23 November 2015	Status:	Final	Novo Nordisk
Study ID: NN8022-4241	EU PAS No.:	Version:	5.0	Page:	23 of 53	

Table 1 - Saxenda® patients¹

Weeks in relation to initiation of treatment/time of first prescription	Prior to treatment initiation	0	4 – 12 weeks	16 – 24 weeks	Throughout the treatment period ²
Visit window			+4 weeks	+4 weeks	
Demography ³		X			
Co-morbidities ⁴	X				
Body Weight		X^5		X^6	
Adult height	X				
BMI		X^5			
Brand name		X			
Indication prescribed		X			
Target dose prescribed		X			
Current dose ⁷			X	X	
Treatment start date		X			
Treatment stop date					X
Concomitant medication with GLP-1					
receptor agonists					X
(Brand name and start date)					

- 1) Inclusion criteria must be fulfilled (incl. obtained informed consent) before data extraction is performed
- 2) Censoring at 24 months after launch
- 3) Sex, age
- 4) Diagnosis of or treatment of pre-diabetes, type 2 diabetes mellitus (T2DM), hypertension, dyslipidaemia and/or obstructive sleep apnoea.
- 5) Latest recording within 6 months before first prescription of Saxenda®
- 6) If not available the earliest subsequent body weight and date of measurement should be recorded
- 7) If treatment discontinuation occurs prior to/between the specified time points, the dose of Saxenda® at time of treatment discontinuation should be recorded.

Protocol		Date:	23 November 2015	Novo Nordisk
Study ID: NN8022-4241		Version:	5.0	
UTN: U1111-1185-3661		Status:	Final	
EU PAS No.:	CONFIDENTIAL	Page:	24 of 53	

Table 2 - Victoza® patients¹

Weeks in relation to initiation of treatment/time of first prescription	0	Throughout the treatment period ²

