Saxenda® patients only:

- Comorbidities:
 - Dysglycaemia (T2DM or prediabetes), hypertension, dyslipidaemia, and/or obstructive sleep apnoea (number and proportion)
- Dose at 4-12 weeks and 16-24 weeks post initiation of treatment (mean, standard deviation)
- Duration of treatment (or ongoing treatment) (mean, standard deviation, median, first and third quartiles and range; number and proportion for treatment completion: completed treatment or ongoing treatment)

Victoza® patients only:

- Increase in Victoza® dose to 3.0 mg/day (number and proportion)
- Prescription of Victoza® for weight management (number and proportion)

Prescription outside label:

Descriptive statistics for the following:

Saxenda® patients:

- BMI<27 kg/m² (number and proportion)
- 27 kg/m²≤BMI<30 kg/m² and no relevant comorbidities registered (dysglycaemia (T2DM or prediabetes), hypertension, dyslipidaemia, and/or obstructive sleep apnoea) (number and proportion)
- BMI not measured within 6 months before date of first prescription (number and proportion)
- Non-adherence to dose escalation according to label (i.e., 3.0 mg not reached within 4-12 weeks after date of first prescription) (number and proportion)
- Non-adherence to stopping rule (i.e., less than 5% weight loss after 16-24 weeks on Saxenda® 3.0 mg and still on continued treatment) (number and proportion)

Protocol		Date:	23 November 2015	Novo Nordisk
Study ID: NN8022-4241		Version:	5.0	
UTN: U1111-1185-3661		Status:	Final	
EU PAS No.:	CONFIDENTIAL	Page:	31 of 53	

• Concomitant medication with other GLP-1 receptor agonists (brand name) (number and proportion)

Victoza® patients:

- Dose information of 3.0 mg per day (number and proportion)
- Prescribed indication of weight management (number and proportion)

All analyses will be performed using SAS 9.2 (or higher) statistical software (SAS Institute Inc., Cary, North Carolina, USA). Programs, logs, and output will be reviewed for accuracy according to relevant standard operating procedures.

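### Two events that can occur at any time on treatment are summarised as raw proportions over 0 to 24 months of follow-up, so they cannot be read as a frequency over a given time on treatment

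*Protocol*

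**What the plan says.** Section 8.7.2 lists "Increase in Victoza® dose to 3.0 mg/day (number and proportion" for Victoza patients and, for Saxenda patients, "Concomitant medication with other GLP-1 receptor agonists (brand name) (number and proportion". Neither has a time horizon or a person-time denominator. Section 7.3 restricts the second event to agonists "prescribed during continued treatment with Saxenda", so stopping Saxenda ends the time at risk. Tables 1 and 2 in section 8.2.6 place both events in the column that covers the whole treatment course.

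On follow-up, the notes to Figure 1 in section 8.1.1 say that "data will be collected on patients from their start date of Saxenda[®]/Victoza[®] until the index date for the full study". The same section says "Data on drug utilisation will be censored on the index date", and puts that date "24 months after launch for the full study". Section 8.2.2 asks only for initiation and consent, and section 8.7.1 analyses all recruited patients. Follow-up can therefore be anything from about 0 to 24 months.

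Section 8.7.2 also says that results will be evaluated by country and by region within country. It sets the main analysis as the proportion of prescriptions outside label over the whole study period, and leaves details to an SAP that is not at hand.

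**The concern.** Both events accumulate with time on treatment. With staggered entry and one calendar cut-off, the proportion who have had the event by the cut-off reflects prescribing and also the calendar time at which patients started. Limiting proportions to non-missing data, as section 8.7 does, does not help, because a patient with one month of follow-up and no event has complete data.

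The protocol handles this elsewhere. Treatment duration has a category for ongoing patients, and the dose and weight endpoints have week windows. These two events have neither. Section 8.9 speaks of 24 months of retrospective follow-up without saying that this is the maximum.

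At stake is the reading of the dose part of the first secondary endpoint and of the concomitant GLP-1 endpoint. A low proportion could mean that such use is rare, or only that most patients started recently. Two countries with identical prescribing but different uptake would show different proportions.

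**Working it through.** The protocol states no event rate, event timing, uptake curve or persistence, so there is no figure of its own to reproduce. All rates and entry patterns below are assumptions.

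**Inputs from the protocol.** Maximum follow-up T = 24 months; minimum none; 150 patients per brand in the full study (section 8.2.1).

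**Formula.** Let f(t) be the density of time to event and F the follow-up. The expected raw proportion is the integral of f(t) × P(F ≥ t) from 0 to T. The comparator is the cumulative incidence at T. With uniform entry P(F ≥ t) = 1 − t/T, so the relative shortfall equals the mean time to event, among events within 24 months, divided by 24. With linearly rising uptake P(F ≥ t) = (1 − t/T)².

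**Step 1: constant hazard, nobody stopping.** Take 5% per patient-year, so a = 0.05 × 2 = 0.1.
- 24-month risk: 1 − exp(−0.1) = 9.5%.
- Uniform entry (mean follow-up 12 months): 1 − (1 − exp(−a))/a = 1 − 0.0952/0.1 = 4.8%, a shortfall of 49%.
- Linearly rising uptake (mean 8 months): 1 − (2/a²)(a − 1 + exp(−a)) = 1 − 200 × 0.004837 = 3.3%, a shortfall of 66%.
- Front-loaded uptake (mean 16 months): 6.4%, a shortfall of 33%.
- Steeper, quadratic uptake (mean 6 months): 2.5%, a shortfall of 74%.

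The same underlying risk of 9.5% thus shows as anything from 2.5% to 6.4%, through entry pattern alone. This is the problem for comparisons between countries and regions. At 10% per year the 24-month risk is 18.1%, against 9.4% (uniform) and 6.3% (rising).

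**Step 2: relax the assumptions.** Shortfall against 24-month incidence:

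| Assumption | Uniform entry | Linearly rising uptake |
|---|---|---|
| On-treatment hazard, median treatment 3 months | 17% | 29% |
| Median treatment 6 months | 29% | 44% |
| Median treatment 12 months | 38% | 54% |
| Median treatment 24 months | 43% | 60% |
| Events spread over first 3 months | 6% | 12% |
| Events spread over first 6 months | 12.5% | 23% |
| Events spread over first 12 months | 25% | 42% |
| Half of the 3.0 mg cases already at first prescription | 25% | 33% |

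The treatment-duration rows use on-treatment incidence as comparator. Front-loaded uptake with events in the first month gives about 0%. Quadratic uptake with a low constant hazard and no stopping gives about 75%.

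**Step 3: does a fixed horizon repair it?** In 4,000 simulated studies of 150 patients (uniform entry, constant hazard, 24-month risk 10%, no stopping), the Kaplan-Meier estimate at 12 months averaged 5.15% against a true 5.13%.

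**Step 4: which horizon can be supported?** With uniform entry and no stopping, the number out of 150 still under observation is 150 × (1 − 6/24) = 112.5 at 6 months, 150 × (1 − 12/24) = 75 at 12 months, 150 × (1 − 23/24) = 6.25 at 23 months, and none at 24. With rising uptake it is 150 × 0.75² = 84 at 6 months and 150 × 0.5² = 37.5 at 12.

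**The case against.** The strongest reply is that the protocol never promises a risk. Its endpoints are numbers of patients and its stated target is a proportion over the study period. Against that target the raw proportion is not biased by length of follow-up. This stands: the issue is what the number can be used for, not that it is computed wrongly.

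A reader might infer that the reported frequencies will be too low by about half or more. The documents do not support that. It needs a 24-month risk as the target, a roughly constant hazard, little stopping, and uniform or late-weighted entry. The GLP-1 endpoint counts only during continued treatment, and section 8.7.2 allows 3.0 mg as a Victoza target dose at first prescription; both reduce the shortfall. Section 6 dates the Victoza authorisation to 2009, so an uptake curve that rises from zero at Saxenda launch has no basis in the documents for that product.

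Two further inferences also fail. Different launch dates do not in themselves distort country comparisons, because each country's index date is tied to its own launch; only the shape of uptake matters. Nor is there a planned comparison of pilot and full-study frequencies: section 8.7.3 describes the pilot report as a qualitative feasibility report.

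The SAP may add a time-based summary, and nothing in the protocol prevents it. But section 8.7.2 does name the summary measure, and names it without a horizon. Finally, with 150 patients, 8 events (5.3%) have an exact 95% interval of 2.3% to 10.2%, so a shift from 10% to 5% is about as large as sampling error. That limits the weight of the point, but sampling error does not remove a systematic dependence on entry pattern.

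**Conclusion.** The point holds in limited form. Staggered entry, no minimum follow-up and a common cut-off mean that these two proportions depend on when patients started as well as on prescribing, and the planned evaluation by country and region inherits this. They are valid as a description of what was recorded in the study period. The shortfall against a fixed-horizon risk cannot be derived from the protocol: it is 49% to 50% for low event rates under uniform entry, constant hazard and no stopping, and about 0% to 75% across the other assumptions tried. This is an inexpensive improvement to two descriptive secondary endpoints, not an error that invalidates the study.

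**What to change.** In section 8.7.2 and the SAP:

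- Keep the raw number and proportion, and report follow-up from first prescription (median and quartiles) beside it, overall and by country.
- Add cumulative incidence at 6 and 12 months from first prescription, censored at the index date and with end of treatment as a competing event (Aalen-Johansen), or else events per patient-year. Do not use 24 months, where essentially nobody remains under observation.
- Report Victoza patients whose target dose was 3.0 mg at first prescription separately, since those cases do not depend on follow-up.
- State in section 8.9 that 24 months is the maximum follow-up.

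For Saxenda, the start and end dates and the start date of the other GLP-1 agonist are already collected (section 8.3). For Victoza, section 8.3 lists dose over the treatment course and repeat prescription dates, but neither it nor Table 2 lists a date of dose increase or of stopping. The date of increase can be derived from those records or recorded in one added CRF field. End of treatment needs a rule based on prescription gaps.

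The cost is one extra table, a derivation rule and possibly one CRF field. The downside is wide intervals with 150 patients per brand.

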8.7.3 Interim analysis

At the end of the pilot study a qualitative pilot study report will be provided to assess the feasibility of the full study. This will include assessment of the number of Saxenda[®] prescriptions identified, taking into account the uptake of Saxenda[®] in the specific country. The availability and quality of the data collected in the pilot for some of the specified endpoints is likely to be limited, especially for adherence to dose escalation, duration of treatment, and adherence to stopping rule. Based on the feasibility assessment, a recommendation will be made on continuation of the study or, if relevant, alternative approaches.

Data on the following endpoints will be captured in the pilot study:

Primary endpoint:

The following endpoints will address the primary objective (concerning Saxenda® only):

BMI and comorbidities:

- Number of patients with BMI\ge 30 kg/m² (measured less than 6 months before date of first prescription)
- Number of patients with 27 kg/m² ≤BMI < 30 kg/m² (measured less than 6 months before date of first prescription) and
 - >=1 relevant comorbidity registered:
 - Dysglycaemia (T2DM or prediabetes), hypertension, dyslipidaemia, and/or obstructive sleep apnoea.
 - o No relevant comorbidities (described above) registered

Protocol		Date:	23 November 2015	Novo Nordisk
Study ID: NN8022-4241		Version:	5.0	
UTN: U1111-1185-3661		Status:	Final	
EU PAS No.:	CONFIDENTIAL	Page:	32 of 53	

- Number of patients with BMI<27 kg/m² (measured less than 6 months before date of first prescription)
- Number of patients with BMI not measured within 6 months before date of first prescription.

Stopping rule:

- Number of patients with at least 5% weight loss (measured 16-24 weeks after first prescription date) and continuing treatment
- Number of patients with less than 5% weight loss (measured 16-24 weeks after first prescription date) and continuing treatment
- Mean weight loss (measured 16-24 weeks after first prescription date) in patients not treated according to stopping rule.

Secondary endpoint

The following endpoint will be used to address the first secondary objective (concerning Victoza® only):

- Number of patients with Victoza® prescriptions fulfilling at least one of the following criteria:
 - o Dose information of 3.0 mg per day, or
 - o Indication of weight management.

The following endpoints will be used to address the second secondary objective (concerning Saxenda® only):

- Adherence to dose escalation according to label:
 - o Number of patients who have reached a dose of 3.0 mg within 12 weeks after first prescription date
- Concomitant medication use of other GLP-1 receptor agonists:
 - o Number of Saxenda[®] patients with other GLP-1 receptor agonists prescribed during continued treatment with Saxenda[®] (continued treatment is defined as no gaps between prescriptions of more than 90 days, identified by examining repeat prescription dates)
- Duration of treatment with Saxenda[®]:

Protocol		Date:	23 November 2015	Novo Nordisk
Study ID: NN8022-4241		Version:	5.0	
UTN: U1111-1185-3661		Status:	Final	
EU PAS No.:	CONFIDENTIAL	Page:	33 of 53	

- Number of patients with a treatment duration of:
 - 0-3, 4-6 months, or ongoing (current patients), with continued treatment defined as no gaps between prescriptions of more than 90 days, identified by examining repeat prescription dates.

8.7.4 Sequential safety analysis/safety monitoring

Not Applicable.

8.7.5 Health economics and/or patients reported outcome

Not Applicable.

8.8 Quality control

This study will be outsourced to a CRO, selected in accordance with Novo Nordisk standard operating procedures (SOPs). The study will be performed by the CRO, with guidance, input, review and approval of Novo Nordisk, including development of materials, recruitment, training and management of sites, site monitoring, EDC and data management and analysis.

8.8.1 Monitoring procedures

During the site initiation visit, the monitor will provide training on the conduct of the study to the physician, and all site staff involved in the study. To ensure the integrity of the data, sites will be monitored by a trained monitor. A risk based monitoring approach will be conducted during the study involving remote data monitoring and ad hoc on site monitoring that will be performed to examine compliance with the protocol and adherence to the data collection procedures, to assess the accuracy and completeness of submitted data, and to verify that records and documents are being properly maintained for the duration of the study. The monitor will perform source data verification by review of original patient records. The physician will allow the monitor to have direct access to appropriate parts of patients' medical records relating to their participation in this study, for the purpose of verifying the data submitted by the site.

The monitor will close out each site after the last patient's data collection is completed, all data have been entered in the CRF and all outstanding monitoring issues have been resolved or addressed.

Representatives of Novo Nordisk and Competent Authorities must be permitted to audit/inspect all study-related documents and other materials at the site, including the Investigator Site File, the completed CRFs and the patients' original medical records. Audits/inspections may be conducted at any time during or after the study to ensure the validity and integrity of the study data.

Protocol		Date:	23 November 2015	Novo Nordisk
Study ID: NN8022-4241		Version:	5.0	
UTN: U1111-1185-3661		Status:	Final	
EU PAS No.:	CONFIDENTIAL	Page:	34 of 53	

8.8.2 Critical documents

Before the physician starts the study (i.e., obtains informed consent from the first patient), the following documents must be available at Novo Nordisk:

- Regulatory approval and/or notification as required
- Documentation of the physician's qualifications as medically qualified (for instance a short CV or authorisation), in addition to qualification documentation of other site staff involved in study conduct
- Signed and dated agreement on the final protocol
- Approval/favourable opinion from Independent Ethics Committee (IEC) (or other appropriate bodies if required locally) clearly identifying the documents reviewed: the protocol, any amendments, patient information/informed consent form and any other written information to be provided to the patient, patient enrolment procedures
- Copy of IEC approved patient information/informed consent form/any other written information/advertisement
- Non-interventional study agreement.

